6.4. Point of enrolment

A subject is considered enrolled in the investigation when the written informed consent is obtained. The expected duration for each subject is described in section 5.9.

6.5. Subject Identification and Confidentiality

Subjects will be identified on the electronic CRF (e-CRF) and any other document transmitted to the sponsor by the principal investigator or clinical site staff, by a unique identification number.

Data entered on the e-CRF are confidential and will only be available to the sponsor (including sponsor delegates), members of the EC and if requested to regulatory authorities.

The principal investigator for each clinical investigation site will maintain as part of the investigational file a list identifying all subjects entered the clinical investigation.

7. Procedures

7.1. Informed consent procedure

Written informed consent is obtained from all subjects participating in the investigation after thorough written and verbal information. The information is given by the investigator or his/her representative in the subjects' native non-technical language. Each subject will be fully informed about the aim of the investigation, procedures, potential risks or inconveniences and/or expected benefits and have a minimum of 24 hours before deciding on participation. The subjects will be informed that their participation is voluntary and that they may leave the investigation at any time, without this having any influence on their further treatment.

The informed consent signature form includes personally dated signatures of the subject and the Investigator or a representative hereof responsible for conducting the informed consent process. A copy will be provided to the subject.

If new information is to be given during the investigation, sponsor will inform the investigators, and the new information is given to the subjects by the investigator. If new information becomes available that can significantly affect a subject's future health and medical care, that information will be provided to the subject in written form. The clinical manager is responsible for writing the information and providing it to the investigators who will further provide it to the subjects. If applicable, all affected subjects shall be asked to confirm their continuing informed consent in writing.

This procedure also applies to informed consent obtained from a subject's legal representative. The procedure cannot waive the subjects' legal rights.

7.2. Secrecy Agreement

In this investigation, there will be a Secrecy Agreement between the subject and Coloplast A/S.

At Coloplast A/S, the aim is to involve the IC users in testing the new catheter concepts. To develop a better product, it is essential for Coloplast A/S to get the user's experiences and comments to the new products as early as possible to receive valuable input for the further development.

Furthermore, it is important for Coloplast A/S to ensure that any new inventions can be patented. To obtain a balance between involving the user at a very early stage and at the same time not waive the rights that Coloplast A/S possess, it has been decided to ask the participants to treat the products and the material they receive from Coloplast A/S in a confidential way.

The confidentiality only concerns the physical materials and information regarding future products, which are delivered by Coloplast A/S and it does not in any way influence other aspects of the user's rights.

The primary purpose of the confidentiality is to ensure that a possible breach of contract will fall under the Danish Patent Act §2(2) and thereby ensure that Coloplast A/S still has the possibility to obtain a patent, and for Coloplast A/S it is not common practice to initiate court cases based on any minor breach of contract.

7.3. Delegation of responsibility and training

Before initiation of the clinical investigation, sponsor must be provided with key personnel signed and dated curriculum vitae (not more than 2 years old) to verify their qualifications. Key site personnel are those, who treat or evaluate subject data in the clinical investigation. Also, the sponsor will ensure that all site personnel are trained in the investigational procedures, how to complete the case report forms (CRFs), procedure for reporting an adverse event (AE) or serious AE (SAE) (how, when, to whom), and who to contact in case of emergency related to the investigational devices. All training and delegation of tasks will be documented in the Clinical Investigation Training log and the Site Personnel Signature and delegation log.

7.4. Clinical investigation-related procedures

Information meeting:

- Subject information. After having received written and verbal information about participation in the investigation, the subject will be offered to have a minimum of 24 hours before deciding on participation (see Informed consent procedure, section 7.1)

Visit 0 (Visit 0 may be completed the same date as visit 1. The subject must wait for 1-2 hours after drinking fluid):

Screening:

- Informed consent, letter of authority and secrecy agreement signed
- In- and exclusion criteria fulfilled (incl. pregnancy test as applicable and dipstick for haematuria, leukocyte and UTI)
- Allocation of subject number and randomisation to order of treatment

Baseline registration:

- Demography (age)
- Concomitant medication
- Relevant medical history

Subject waits 1-2 hours after drinking fluid

Collection of total urine for analysis of [REDACTED]

- Haematuria and leukocytes measured by dipstick

Test visits 1-3 (Expected duration is approximately 3.5 hours per visit):

- Symptoms of UTI (The Investigators Judgement)
- Catheterisation by nurse with relevant catheter (including pressure sensor and time-logged weighing of urine). Each catheterisation lasts approximately 15 minutes in total.
- Residual Urine measured (by ultrasound scan)
- Inspection of urine running outside the catheter
- Inspection of visual blood on catheter

Collection of total urine for analysis of [REDACTED]

- Haematuria and leukocytes measured by dipstick

- Discomfort registered by subject (VAS scale) (insertion, during voiding, withdrawal, overall)
- The nurse evaluates the overall handling of the catheter

Subject waits 1-2 hours after drinking fluid

- Subject self-catheterises with relevant catheter (collection of urine before/after first repositioning including pressure sensor and time-logged weighing of urine)
- Residual urine measured (by ultrasound scan)
- Inspection of urine running outside the catheter
- Inspection of visual blood on catheter

[REDACTED] Collection of total urine for analysis of [REDACTED]

- Haematuria and leukocytes measured by dipstick
- Discomfort registered by subject (VAS scale) (insertion, during voiding, withdrawal, overall)
- The subject evaluates the overall handling of the catheter
- Registration of AE as applicable
- Schedule next visit (as applicable)

[REDACTED]
[REDACTED]
[REDACTED]
[REDACTED]
[REDACTED]

Termination visit

- Perform device accountability

[REDACTED] Collection of total urine for analysis of [REDACTED]

- Haematuria and leukocytes measured by dipstick
- Registration of AE as applicable
- Complete termination form

[REDACTED]
[REDACTED]

7.6. Rescheduling of visit

7.6.1. Suspicion of urinary tract infection

If the subject shows symptoms of UTI as judged by the investigator after she has been enrolled in the investigation, his visit can be rescheduled if possible and preferably before planned LPO visit, when the subject has been examined and treated for potential UTI and shows no symptoms afterwards. If it is not possible to complete all visits before LPO, the subject should complete as many visits possible allowed according to the investigation timelines.

7.6.2. Use of analgesics

Concomitant medication including analgesics should be noted, and the subject should not have changed their medication the last 24 hours before test visit 1-3 and during home use.

7.7. Activities performed by sponsor representatives

Sponsor (Clinical Manager or a representative hereof) is responsible for:

- Training of the investigator and investigational personnel in the informed consent procedure, investigation procedures, how to use the products, how to perform accountability of products, completing of the CRF, how to report possible safety issues and in ISO 14155. All training will be documented
- Support during the recruitment process and conduct of the investigation
- Measurements with pressure sensor
- Transportation of collected urine from site to Coloplast
- On site help with practicalities
- General support during the duration of the investigation
- Monitoring according to monitoring plan

7.8. Flow-chart

PER-FORMED BY	INFORMATION MEETING	V0	V1	V2	V3		TERMINATION VISIT
---------------	---------------------	----	----	----	----	--	-------------------

CONFIDENTIAL

Visit window	-	The subject is offered to have a min. of 24 hours before deciding on participation	-	0-21 days	4-14 days	4-14 days	5-21 days	
General								
Subject Information	Investigator	X						
Signed Informed Consent	Subject		X					
Signed letter of Authority and secrecy agreement	Subject		X					
Check of in- and exclusion criteria	Investigator		X					
Pregnancy test as applicable	Investigator		X					
Allocation of subject number and randomization order	Investigator		X					
Check subject's well-being and compliance with Clinical Investigation plan	Investigator		X	X	X	X		
Registration of Baseline data								
Demography (age)	Investigator		X					
Concomitant medication	Investigator		X					
Relevant medical history	Investigator		X					
Drink fluid and wait for approximately 1-2 hours	Subject		X					
	Subject		X					
Procedures								
Symptoms of UTI (Investigators Judgement)	Investigator			X	X	X		
Catheterisation by nurse	Investigator			X	X	X		
	Investigator			X	X	X		
Clogging events measured by sensor	Investigator / CP employee			X	X	X		
Residual urine measured by bladder scan	Investigator			X	X	X		
Inspection of visual blood on catheter	Investigator			X	X	X		
Registration of urine running on the outside of catheter	Investigator			X	X	X		
	Investigator / CP employee			X	X	X		

Haematuria and leukocytes measured by dipstick (post-catheterisation)	Investigator			X	X	X		
Discomfort registered by subject (VAS) post catheterisation	Subject			X	X	X		
The nurse evaluates the overall handling of the catheter	Investigator			X	X	X		
Drink fluid and wait for approximately 1-2 hours	Subject			X	X	X		
Subject self-catheterises with relevant catheter	Subject			X	X	X		
Residual urine measured (by ultrasound scan)	Investigator			X	X	X		
[REDACTED]	Subject			X	X	X		X
Inspection of urine running outside the catheter	Subject			X	X	X		
Inspection of visual blood on catheter	Investigator			X	X	X		
Haematuria and leukocytes measured by dipstick (post self-catheterisation)	Investigator / CP employee			X	X	X		X
Discomfort registered by subject (VAS) self-catheterisation	Subject			X	X	X		
The subject evaluates the overall handling of the catheter	Subject			X	X	X		
Registration of any Adverse Events	Investigator			X	X	X		X
Complete eCRF	Investigator			X	X	X		X
Schedule next visit	Investigator			X	X	X		
[REDACTED]	Investigator						X	
[REDACTED]	Investigator							X
Perform device accountability	Investigator							X
Registration of termination								X
Complete Termination form	Investigator							X

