5.8. Blinding

Subjects will not be blinded in this investigation due to inclusion of self-catheterisation. Furthermore, personnel present at the catheterisation i.e. nurses and assisting Coloplast personnel are also not blinded. Coloplast personnel not present at the catheterisation i.e. the statistician will be blinded until the data base lock.

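### The flow-chart lets a sponsor employee read the haematuria and leukocyte dipsticks after self-catheterisation but not after nurse catheterisation, and section 7.7 does not list this task

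*Combined protocol and SAP*

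**What the plan says.** Section 7.8 has one dipstick row for each type of catheterisation, and the performer differs:

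- Nurse block, visits 1 to 3: "Haematuria and leukocytes measured by dipstick (post-catheterisation) Investigator".
- Self-catheterisation block, visits 1 to 3 and termination: the row "Haematuria and leukocytes measured by dipstick (post self-catheterisation", where the performer entry is Investigator / CP employee.

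The only other row with a readable label that is open to a CP employee is the sensor row: "Clogging events measured by sensor Investigator / CP employee". Section 7.4 lists the dipstick after both catheterisations without naming a reader.

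Section 7.7 sets out what sponsor representatives do. It names one measurement, "Measurements with pressure sensor", and one task with urine, "Transportation of collected urine from site to Coloplast". The rest is training, support, monitoring and "On site help with practicalities".

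On blinding, sections 5.8 and 10.2 state that "personnel present at the catheterisation i.e. nurses and assisting Coloplast personnel are also not blinded".

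Positive haematuria and positive leukocytes on dipstick are exploratory endpoints (5.4), and section 5.5 treats these measures as safety indicators. Section 10 plans analysis by catheterisation type where the data allow. Section 10.5 models the dipstick counts with the same effects as the primary model, that is visit, treatment and subject. There is no term for the reader.

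**The concern.** One endpoint should have one reader rule. Here the rule changes exactly where the plan intends to make a comparison, between nurse catheterisation and self-catheterisation. If sponsor staff read the self-catheterisation strips, a difference between the two types could come from the reader and not from who inserted the catheter.

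The device comparison is exposed in a different way. A reader with a uniformly stricter or looser threshold does not by that fact favour one device. A reader whose calls depend on the product does, and a sponsor employee who assists at the catheterisation knows which catheter was used. Randomised order and the visit effect do not remove this, because the knowledge follows the product from visit to visit. The reader would also be employed by the manufacturer of the devices under test, a conflict of interest that the nurse block avoids.

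**Working it through.** The plan gives no figure on this point and no formal sample size calculation (10.6), so there is nothing to reproduce. The check is a count of scheduled readings by permitted reader.

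**Inputs.** 15 completers (section 6); three test visits, each with one nurse catheterisation and one self-catheterisation, and a dipstick after each (7.4, 7.8); permitted readers from the performer column of 7.8.

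**Count per analyte.**

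| Readings | Per subject | 15 completers | Open to sponsor reader |
|---|---|---|---|
| After nurse catheterisation, visits 1–3 | 3 | 15 × 3 = 45 | 0 |
| After self-catheterisation, visits 1–3 | 3 | 15 × 3 = 45 | up to 45 |
| Total, visits 1–3 | 6 | 90 | up to 45 (3/6 = 50%) |
| Adding termination | 7 | 105 | up to 60 (4/7 = 57%) |

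Per device there are 30 readings at visits 1 to 3, of which up to 15 are open to a sponsor reader. Section 10.6 expects 2 to 3 drop-outs. If they were not replaced, the counts would be 39 of 78 (13 subjects) or 36 of 72 (12 subjects), and the share would still be half.

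**By stratum.** In the analysis by catheterisation type the share is up to 45/45 = 100% of the self-catheterisation readings and 0/45 = 0% of the nurse readings.

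**Sensitivity to single calls.** In the self-catheterisation stratum one changed call moves a device's rate by 1/15 = 6.7 percentage points, and two move it by 2/15 = 13.3 points. Pooled over both types, one call moves it by 1/30 = 3.3 points.

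**How a bias would carry through (assumed values, not in the documents).** Let d be the difference between devices in misreading rate, with sponsor staff reading every self-catheterisation strip and no such difference in the nurse readings. The shift is d in the self-catheterisation stratum and d × 3/6 when pooled. For d of 5, 10 or 20 points, the pooled shift is 2.5, 5 or 10 points. This shows scaling only; nothing in the documents indicates a value for d.

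**After the change.** Readings open to a sponsor reader at visits 1 to 3 fall from up to 45 of 90 to 0 of 90.

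**The case against.** The case for leaving the plan alone has several parts.

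- *Section 7.7 is not exclusive.* It includes general on-site help and support during conduct, and section 5.8 openly mentions assisting sponsor staff. This stands. A reader might infer that 7.8 breaches a prohibition in 7.7, but there is none. The task is unlisted, in a section that does name the sensor measurement.
- *Site readers are unblinded too.* This stands. Unblinded-reader bias can enter all 90 readings. What changes with the row is the reader's employer and the consistency of the rule.
- *The chart may be imperfect.* One further row open to a CP employee has no readable label, and the self-catheterisation block has no readable sensor row although 7.4 uses the sensor there. A misplaced performer entry is possible. The termination mark on the dipstick row agrees with 7.4, which supports the row's visit marks but does not prove its performer cell. CP employee is also not defined in the abbreviations; a sponsor employee fits the sensor row and 7.7. If the entry is a slip, the same edit corrects it.
- *Attribution is already required.* Section 9.4 makes the principal investigator responsible for attribution of reported data, and section 1.3 requires delegated site tasks to be documented. A reader might infer that nobody could tell who read a strip. The documents do not support that, although no reader field for each strip is named.
- *The endpoints are exploratory.* This stands and limits the severity. Section 10.7 nevertheless says that any endpoint's outcome informs device development.

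**Conclusion.** The inconsistency is real and worth correcting, as a minor point. Sections 7.7 and 7.8 do not agree on whether sponsor staff read dipsticks, and 7.8 applies different reader rules to the two types of catheterisation. At most 45 of 90 readings per analyte at visits 1 to 3 are affected. This is an upper limit, because the cell permits a sponsor reader and does not require one. It rests on 15 completers and on reading CP employee as a sponsor employee.

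A reader might infer a measurable bias of so many points in favour of the new devices. The documents do not support that. They do not say how the strips are read (by eye or by instrument), give no cut-off for a positive result and do not say how often sponsor staff would read. The gain from the change is only the difference between sponsor and site reader bias, which cannot be estimated. A reader might also extend the point to visible blood and leakage, but section 7.8 already assigns those inspections to the investigator or the subject. The primary and secondary endpoints are not touched by this point.

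**What to change.** In the section 7.8 row for the dipstick after self-catheterisation, replace the entry Investigator / CP employee with Investigator (site nurse or delegate), as in the nurse block. Add one sentence to section 7.7 stating that sponsor representatives do not read dipsticks.

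The cost is one table cell and one sentence. Site staff already read the other strip at the same visit, so no new procedure is needed. The limitation is that site readers know the device as well; removing that bias would need a reader masked to the device, which is a larger step. An optional addition is an eCRF field for who read each strip, so that reader effects could be checked afterwards.

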7.9. Case Report Forms

All assessments and observations throughout the investigation for each subject must be carefully recorded in an electronic CRF (eCRF) on a PC provided to the site by Coloplast.

Assessments completed by the investigator, or delegate, will be recorded in the eCRF.

CRFs will be completed by the investigator, or delegate, who has signed the Site Personnel Signature and Delegation List and Clinical Investigation Training Log.

It is the responsibility of the investigator that all data, measurements and observations are entered promptly and correctly and preferably immediately after the subject has been at site.

7.10. Supplementary materials and equipment

Supplementing devices or instruments normally used for catheterisation (e.g. medical gloves, tray for urine collection), scales for measurement of total amount of urine, ultra sound scanner measuring residual urine-container and funnel for urine collection and CE-marked commercially available SpeediCath® standard catheter acting as comparator and pressure sensor to measure coggings.

The pressure sensor is an electronic device used for monitoring the pressure at the outlet of an intermittent urinary catheter voiding. The pressure sensor comprises a reusable electronic assembly and a single use adaptor which connects the catheter to the sensor. None of the sensor parts will have direct nor indirect contact to the end-user. The investigator is required to use gloves during the handling of the pressure sensor device during catheterisation.

The pressure sensor with the same functionality, hardware and specifications has previously been used in a Coloplast clinical investigation (CP304) [7].

8. Risk – benefit analysis and ethical considerations

The investigation is conducted in accordance with current law and applicable standards, see section 15. Statement of Compliance. The rights, safety and well-being of human subjects shall prevail over the interest of science of society.

The catheterisation of the subjects, with both investigational devices and the comparator catheter will be performed by experienced urology nurses at sites with many years of experience in conducting IC and with previous experience in working with clinical investigations.

There are no direct benefits for the subjects involved; but, by participating in this investigation, the subjects will contribute with important information for developing improved solutions for urinary IC that in turn may benefit individuals who are dependent on catheters for emptying their bladder.

The investigation is conducted in accordance with 'The Declaration of Helsinki', 1964, last amended at the 64th WMA General Assembly, Fortaleza, Brazil, October 2013, and ISO 14155 and the Medical Device Directive/Regulation.

Completed pre-clinical and clinical studies on the new catheter concept did not reveal any additional risks associated with the catheter prototypes [8]. Risks associated with the investigation may be discomfort or stinging in the urethra during the catheterisation. Furthermore, there may be a risk of micro-trauma and haematuria and leukocytes after catheterisation, which is expected to heal within 1-3 days. The investigational setting is not expected to result in increased frequency or severity of the known risks associated with urethral catheterisation.

9. Monitoring Plan

The sponsor is responsible for ensuring appropriate monitoring of the clinical investigation activities.

During the period of this investigation, monitoring is planned and carried out by the Clinical Managers.

The monitor (Clinical Manager) will be the primary contact for the investigator and clinical investigation site personnel.

Monitoring activities are mandatory as per good clinical practice, however the extend and depth of these activities depend on the criticality of the clinical investigation, speed of enrolment, the experience of the clinical investigation site personnel in carrying out clinical investigations and specific study designs.

For the purpose of this clinical investigation the below described monitoring procedures have been determined.

